#### **7.7.2. Change in Dimple Analysis Parameters using 3-D Photographic Image**

The observed and change from Day 1 pre-marking image in dimple analysis parameters, max length, max width, surface area, and volume between the dimple base and interpolated surface, will be summarized at Day 22, 43, and 71/ET by treatment area and treatment arm using descriptive statistics.

In addition, the volume and depth data will be analyzed using the linear mixed effect model described in Section 7.7.1.1.

A listing of dimple analysis parameters will be provided.

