17.5. Efficacy Analyses

The efficacy endpoints for this study will include:

- Change from baseline in the blinded assessor's Likert Scale score of aesthetic appearance in each treatment area (buttocks or thighs) at Days 22, 43, and 71 by each treatment arm.
- Change from baseline in dimple depth and volume in each treatment area (buttocks or thighs) Days 22, 43, and 71 by treatment arm.
- Change from baseline in the Hexsel CSS (B) depression depth scale at Days 22, 43, and 71 by treatment arm.

The central assessor Likert Scale score of aesthetic appearance improvement from baseline in the 3-D photographic image, change from baseline in the Hexsel CSS (B) depression depth scale, and change from baseline in dimple volume and depth will be summarized by treatment arm and study visit using appropriate descriptive statistics. In addition, a linear mixed model will be utilized to fit change from baseline of each endpoint with treatment arm, cellulite dimples, and study visit as fixed effects, subject as random effect, and assessments across study visits as repeated measure. The fixed effect estimates and the corresponding 95% confidence intervals will be presented for each endpoint.

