### 3.9. Dimple Analysis

The Image Analysis Technician (IAT) will use the Day 1-Post marking image as a reference to determine the location of the target dimple on the Day 1-Pre marking image.

A tracing will be made around the border of concavity of the dimple on the Day 1-Pre marking.

The dimple tracing will be transposed on to the Day 22-Pre Marking, Day 43-Pre marking, and Day 71/ET images.

This tracing will be used to measure the:

- Max length, the largest straight line distance across the dimple
- Max width, the largest straight line distance perpendicular to the max length measurement
- Surface area of the dimple
- Volume between the base of the dimple and the interpolated surface

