##### **4.5.2. Change in Dimple Analysis Parameters using 3-D Photographic Image**

Dimple analysis parameters, max length, max width, surface area and volume between the dimple base and interpolated surface, will be assessed by IAT in each treatment area at Day 1, Day 22, 43, and 71/ET. The change in these parameters from Day 1 will be evaluated at Day 22, 43, and 71/ET.

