## **6.2. Adjustments for Covariates**

Not applicable.

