### **7.7.1. Improvement in Aesthetic Appearance using 3-D Photographic Images**

#### **7.7.1.1. Analysis of Treatment Region and Area**

The Likert Scale score of improvement in aesthetic appearance from baseline will be analyzed using a linear mixed model with treatment arm, study visit, interaction of treatment arm and study visit as fixed effects. The fixed effect estimates and 95% CIs for interaction effect of treatment arm and study visit will be presented. This model will be fitted using the response for each treatment area (ie, left buttock, right buttock, left thigh, and right thigh) and for the average of left and right of treatment area (ie, average of left buttock and right buttock; average of left thigh and right thigh).

The Likert Scale rating of improvement in aesthetic appearance from baseline will also be summarized using count and percentage by treatment arm and study visit/day (Day 22, 43, and 71) for each treatment area and with mean and SD.

A listing of Likert Scale scores will be provided.

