**Table 13: Changes from Protocol**

Text in Protocol	Change in SAP	Justification
a linear mixed model will be utilized to fit change from baseline of each endpoint with treatment arm, cellulite dimples, and study visit as fixed effects, subject as random effect, and assessments across study visits as repeated measure. The fixed effect estimates and the corresponding 95% confidence intervals will be presented for each endpoint.	The Likert Scale score of improvement in aesthetic appearance from baseline will be analyzed using a linear mixed model with treatment arm, study visit, interaction of treatment arm and study visit as fixed effects. The fixed effect estimates and 95% CIs for interaction effect of treatment arm and study visit will be presented. This model will be fitted using the response for each treatment area (ie, left buttock, right buttock, left thigh, and right thigh) and for the average of left and right of treatment area (ie, average of left buttock and right buttock; average of left thigh and right thigh).	Clarify the same model will fit to the response for each treatment area. Remove the covariate of cellulite dimples from the model as the number of dimples treated is not play an role

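### The dimple-volume change model leaves out Day 1 volume, which is already measured; adding it is a cheap improvement for that endpoint

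*SAP*

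**What the plan says.** SAP 7.7.1.1 analyses the Likert score "using a linear mixed model with treatment arm, study visit, interaction of treatment arm and study visit as fixed effects". It is fitted to each treatment area and to the left-right average. SAP 7.7.2 reuses it for image-based dimple data: "the volume and depth data will be analyzed using the linear mixed effect model described in Section 7.7.1.1".

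Section 7.7.2 does not say in that sentence whether the modelled volume is the observed value or the change. SAP 4.5.2 points to change: "The change in these parameters from Day 1 will be evaluated at Day 22, 43, and 71/ET". So does protocol 17.5: "a linear mixed model will be utilized to fit change from baseline of each endpoint".

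The baseline exists. SAP 3.9 has the dimple border traced on the Day 1 pre-marking image and carried to later images. Among the measurements it lists is "Volume between the base of the dimple and the interpolated surface". SAP 6.2, headed "Adjustments for Covariates", says only that this is not applicable.

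For display, the observed values and changes "will be summarized at Day 22, 43, and 71/ET by treatment area and treatment arm using descriptive statistics". A subject listing of the dimple parameters is also promised. Day 1 volume is not among the baseline characteristics in SAP 7.3.

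**The concern.** A model built for an endpoint without a baseline is carried over to one that has it. Likert is already a rating of improvement, so no baseline term was possible there. Volume is different: a larger dimple has more volume to lose, so change may depend on Day 1 size.

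Each regional fit compares five arms of 6 subjects. Arms that small will often differ in Day 1 volume by chance, and an unadjusted change score passes part of that difference into the arm-by-visit estimates. A repeated-measures covariance or a subject effect does not remove it, because the Day 1 value is not in the modelled response. At stake are the precision and steadiness of the model-based comparison of techniques, which serves the primary objective.

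**Working it through.** **Inputs from the documents.** Five arms, 6 subjects per arm per region (SAP 3.1); 95% intervals (SAP 6.1). The plan gives no power, SD or correlation, so it has no figure on this point to reproduce.

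**Assumptions.** One region, one visit, complete data. Rho is the correlation between Day 1 and follow-up volume; k is baseline SD divided by follow-up SD. Both are assumed ranges.

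**Step 1: chance imbalance.** The difference between two arm means at baseline has SD sqrt(2/6) = 0.577 baseline SD.
- Given pair: expected absolute difference 0.577 × sqrt(2/π) = 0.46 SD; probability of at least 1 SD, 0.08.
- Most extreme of the ten pairs: expected range 2.326/sqrt(6) = 0.95 SD; probability of at least 1 SD, 0.41.

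**Step 2: effect on the unadjusted contrast.** A baseline difference of d SD shifts the change contrast, in size, by |rho − k| × d follow-up SD. With k = 1 and rho 0.3, 0.5, 0.7:
- d = 0.46: 0.32, 0.23, 0.14.
- d = 0.95: 0.66, 0.47, 0.28.

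**Step 3: interval width.** In units of follow-up variance, the change score has variance 1 + k² − 2·rho·k on 25 df. The adjusted response has variance (1 − rho²) × 24/23 on 24 df, where 24/23 is the average cost of estimating the slope. The half-width for a pair is t × sqrt(variance × 2/6), with t = 2.0595 (25 df) and 2.0639 (24 df). For k = 1:

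| rho | planned | adjusted | ratio |
|---|---|---|---|
| 0.3 | 1.41 | 1.16 | 0.83 |
| 0.5 | 1.19 | 1.05 | 0.89 |
| 0.7 | 0.92 | 0.87 | 0.94 |
| 0.8 | 0.75 | 0.73 | 0.97 |
| 0.9 | 0.53 | 0.53 | 1.00 |
| 0.95 | 0.38 | 0.38 | 1.01 |

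Break-even is near rho = 0.91. Simulation at rho 0.3, 0.5, 0.7 and 0.9 gave ratios of 0.83, 0.89, 0.94 and 1.00, with about 95% coverage for both models.

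If the SDs differ, the ratios at rho 0.3, 0.5, 0.7 are 0.73, 0.77, 0.81 for k = 1.25 and 0.93, 0.98, 1.02 for k = 0.75.

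**Step 4: cost when there is no gain.** This is the case rho = k, where change is unrelated to baseline.
- Average: sqrt(24/23) × 2.0639/2.0595 = 1.024. With 5 per arm: sqrt(19/18) × t(19 df)/t(20 df) = 1.031.
- A pair 0.95 SD apart: sqrt(1 + 0.95²/((2/6) × 25)) × 2.0639/2.0595 = 1.055.
- The most imbalanced pair, by simulation: mean 1.066, 90th percentile 1.13.

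**Step 5: Hexsel.** Qualifying dimples score 2 or 3 at entry, which limits baseline spread if area scores follow. With k = 0.5 as an illustration, the ratios at rho 0.3, 0.5, 0.7 are 1.00, 1.02, 0.99.

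**The case against.** The strongest reply is that nothing is broken. The study is exploratory with no sample-size calculation, a change-score model gives valid intervals, and choosing it over baseline adjustment is a matter of efficiency. One tracing carried across visits could make rho high, and above about 0.9 (equal SDs) the gain is gone. For badly imbalanced pairs, adjustment can widen the interval by clearly more than 2.4%. All of this stands and limits the point to an improvement.

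Four stronger readings are tempting, and the documents do not support them.
- *A Day 1 volume imbalance would be hidden.* SAP 7.7.2 promises a listing of the dimple parameters, and SAP 4.5.2 names Day 1 as an assessed visit, so values should be visible by subject. What the text does not name is a summary by arm; the table shells are in SAP Module 2, which is not among the documents reviewed.
- *Table 13 should have justified omitting baseline.* It records departures from the protocol, and the protocol model never contained the baseline value. The term it removes is another one: "Remove the covariate of cellulite dimples from the model as the number of dimples treated is not play an role".
- *Adjustment would repair the allocation.* Assignment is sequential and open-label. Adjustment handles chance imbalance in the measured baseline, not systematic differences between arms. Nothing in the documents ties arm order to baseline severity.
- *Hexsel needs the same change.* Step 5 shows that the gain there may be nil.

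**Conclusion.** The point holds for dimple volume, as a low-cost improvement rather than the correction of an error. The model omits a baseline that is already measured, and the sections cited give no statistical reason for leaving it out. With equal SDs, adjustment would shorten the average interval by 17%, 11% or 6% at rho 0.3, 0.5 or 0.7, by 3% at 0.8, and by nothing from about 0.9. The average cost is at most about 2.4% (3.1% with 5 per arm), with larger losses for very imbalanced pairs when there is no gain. These sizes rest on assumed values of rho and k, and on reading 7.7.2 as an analysis of change. A reader might infer that the planned intervals are wrong; they are not, since their coverage over repeated trials is about 95%. The Likert analysis is unaffected. The depth variable named in 7.7.2 is not among the SAP 3.9 measurements, so the point does not extend to it as the text stands.

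**What to change.** In SAP 6.2 and 7.7.2, add Day 1 pre-marking volume and its interaction with visit to the volume-change model. Form the covariate in the same way as the response: the same area in single-area fits, the left-right average in average fits, and the same handling of the two selected dimples per area. Summarise Day 1 volume by arm. Record the change in Table 13. Keep the unadjusted fit as a sensitivity analysis. For Hexsel, baseline adjustment can be an optional sensitivity analysis only.

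The cost is SAP wording and minor programming, with no new data or visits; statistically, it is one degree of freedom per visit and the widening shown in step 4. SAP version 2.0 is dated 11 February 2019, after the protocol's estimated January 2019 completion of the last subject. The documents do not show whether outcome data had been seen. If they were seen before this change, label the adjusted fit as a later addition and present both fits side by side.

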#### **7.7.3. Change from Baseline in Dimple Depth Depression by Hexsel CSS (B)**

The change from baseline in the Hexsel CSS (B) depression depth scale for each treatment area at Days 22, 43, and 71 will be analyzed and summarized as described in Section 7.7.1.1.

In addition, a shift table of Hexsel CSS (B) depression depth evaluation at baseline and post baseline study visit/day will be presented using counts and percentages.

A listing of Hexsel CSS (B) values will be provided.

## **7.8. Safety Analyses**

Safety data will be summarized by treatment arm and by treatment region (ie, Buttocks, Thighs, and Overall) using the Safety Population.

### **7.8.1. Study Drug Exposure**

The number of injections of study drug given on Days 1, 22, and 43, will be summarized per treatment area and by treatment arm using counts and percentages as:

- Subjects who received 12 injections per treatment area
- Subjects who received less than 12 injections per treatment area along with reason

The following will be summarized at each treatment visit by treatment area and treatment arm using descriptive statistics:

- Number of injections given
- Number of dimples treated
- Average number of injections per dimple
- Duration of exposure (refer to [Table 12](#) for computation of exposure duration)

The number of subjects treated at each treatment visit will be summarized using frequency count and percentage by treatment area and treatment arm.

A subject listing of overall exposure, and injection status will be provided along with the reasons for receiving less than 12 injections per treatment area.

### **7.8.2. Adverse Events**

All AE summary tables will include only TEAEs, unless otherwise specified.

AEs will be summarized by SOC and PT. A subject will only be counted once per SOC and PT.

For AEs by severity grade (mild, moderate, severe), if a subject has multiple events occurring in the same SOC or same PT, then the event with the maximum intensity (ie, severe) will be counted.

For AEs by relationship to study drug, if a subject has multiple events occurring in the same SOC or same PT, the event with the highest association (ie, related) to study drug will be summarized.

AEs will be presented in decreasing order of the incidences at SOC level and within each SOC, in decreasing order of the incidences at the PT level.

An overall summary of AE and AE related to study drug will be presented and will include:

- Total number of TEAEs reported
- Total number of TEAEs reported by severity
- Total number of AEs of special interest
- Subjects with any TEAE
- Subjects with any special interest AE
- Subjects with any serious TEAE
- Subjects with any severe TEAE

- Subjects with no severe TEAEs, but at least one moderate TEAE
- Subjects with no severe TEAEs, but at least one mild TEAE
- Subjects with any TEAEs leading to drug interruption/withdrawn
- Subjects with any TEAEs leading to study discontinuation
- Subjects with any TEAEs resulting in death

The following summary tables will be presented by SOC and PT:

- All TEAEs
- TEAEs by severity
- TEAEs by relationship to study drug
- All non-study drug related TEAEs
- All study drug related TEAEs
- Study drug related TEAEs by severity
- Serious TEAEs
- Serious study drug related TEAEs
- Duration of study drug related TEAEs (<14 days, 14 – 21 days and >21 days)
- TEAEs leading to drug interruption/withdrawn
- Study drug related TEAEs leading to drug interruption/withdrawn
- TEAEs leading to study discontinuation
- Study drug related TEAE leading to study discontinuation
- TEAEs resulting in death
- Study drug related TEAEs resulting in death
- AEs of special interest

Serious and most common non-serious TEAE by order of frequency (Most frequent, 2nd most frequent, and 3rd most frequent) will be summarized by PT. Most common non-serious AEs are any preferred term that at least 5% of the subjects reported at least once.

The following listings will be presented by subject:

- All AEs
- Serious AEs
- AEs resulting in drug interruption/withdrawn
- AEs resulting in study discontinuation
- AEs resulting in deaths
- AEs of special interest

Refer to [Table 12](#) for computation of duration of AEs.

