8.3. Summary of Known Risks and Benefits

A summary of safety risks is provided in the IB (Endo, 2017). The following AEs have been commonly observed: local injection site reactions (including injection site bruising, injection site swelling, and injection site pain) for the various approved indications as well as those being investigated.

In the Phase 2b study of CCH in women with EFP, the following treatment related AEs were reported $\geq 2\%$ of 189 CCH-treated female subjects: injection site bruising (75.1%), injection site pain (59.3%), injection site nodule (14.3%), injection site pruritus (11.1%), injection site swelling (7.4%), injection site induration (5.8%), injection site mass (5.3%), injection site

discoloration (3.2%), and injection site erythema (2.1%). These events are similar to events reported in the clinical trials of EN3835 for the approved indications.

Postmarketing safety data are consistent with safety data reported in clinical trials. AEs reported to date in ongoing Phase 3 trials of CCH for the treatment of EFP of the buttocks have not indicated any new safety signals.

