9.2. Secondary Objective

The secondary objective of this study is to assess the safety of CCH when administered using different injection techniques in subjects with EFP.

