17.6.4. Adverse Events

The Medical Dictionary for Regulatory Activities (MedDRA) will be used to code AEs.

An AE (classified by preferred term) that started on or after the date of the first dose of the study drug will be considered a TEAE if it was not present prior to the first dose of study drug, or was present prior to the first dose of study drug but increased in intensity during the treatment period. If more than 1 AE is reported prior to the first dose of study drug and coded to the same

preferred term, then the AE with the greatest intensity will be used as the benchmark for comparison to the AEs occurring during the treatment period which were also coded to that preferred term. Any AE present prior to the first dose of study drug that increases in intensity during the treatment period will be re-entered with a new start date of the date of increased intensity.

Descriptive statistics (the number and percentage) for subjects reporting TEAEs in each treatment arm will be tabulated by system organ class and preferred term; by system organ class, preferred term, and severity; and by system organ class, preferred term, and relationship to study drug. If more than 1 AE is coded to the same preferred term for the same subject, the subject will be counted only once for that preferred term using the most severe and most related occurrence for the summarization by severity and by relationship to the study drug.

Listings will be presented for subjects with SAEs, subjects with AEs leading to discontinuation of study or study drug, and subjects who die (if any).

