## **3. STUDY DESIGN AND MEASURES**

### **3.1. Study Design**

This is a Phase 2a, open-label, multicenter, exploratory study to evaluate the safety and effectiveness of different injection techniques of CCH for the treatment of adult women with EFP. This study will be performed at approximately 5 sites in the United States (US).

Subjects having the evidence of cellulite in 2 buttocks or 2 thighs (treatment area) at the Screening Visit will be enrolled if they satisfy the criteria below:

- Have a CR-PCSS score of 2 (mild), 3 (moderate) or 4 (severe) as reported by the Investigator in 2 treatment areas (two thighs or two buttocks)
- Have at least 2 dimples from each treatment area that:
  - are isolated and separated by at least 5 cm from any other dimples

- score 2 or 3 on the Hexsel depression scale
- have dimple width: length ratio  $\geq 0.5$

If both buttocks and both thighs meet entry criteria for a single subject, then the thighs will be treated. No subject will be treated for EFP in both the buttocks and the thighs during this study.

The study will enroll approximately 60 subjects; 30 subjects with 2 eligible buttocks (to be dosed in the buttocks) and 30 subjects with 2 eligible thighs (to be dosed in the thighs). The 30 subjects in each treatment region (buttocks or thighs) will be assigned sequentially to 1 of 5 injection technique treatment arms on Day 1 (ie, 6 subjects per region per treatment arm). No control groups will be employed. Subjects who discontinue from the study will not be replaced.

Subjects who complete the study will participate for approximately 92 days including a 21-day of screening period, a 43-day treatment period and a 28-day follow-up period. Subjects will receive the study injections on Days 1, 22, and 43. Additional scheduled assessments will be performed on Days 4, 8, 15, and 71.

[Table 1](#) below describes the schedule of events and assessments performed during screening, treatment visits, and assessment visits.

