### **3.4. Treatment Region and Area**

Treatment region is defined as buttocks OR posterolateral thighs. A subject will have two treatment areas defined as both buttocks (left and right buttocks) OR both thighs (left and right posterolateral thighs).

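### Once-per-subject adverse-event counts over up to three sessions discard recurrence of bruising and pain, and no preferred-term table shows reactions by session

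*SAP*

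**What the plan says.** SAP 7.8.2 states the counting rule: "A subject will only be counted once per SOC and PT". Protocol 17.6.4 has the same rule at preferred-term level. When several events share a term, "the subject will be counted only once for that preferred term using the most severe and most related occurrence". SAP 7.8 sets the breakdown: "Safety data will be summarized by treatment arm and by treatment region (ie, Buttocks, Thighs, and Overall) using the Safety Population". Neither document calls for an adverse-event table by treatment session or by left and right area.

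The design gives repeated exposure. SAP 3.1: "Subjects will receive the study injections on Days 1, 22, and 43". SAP 3.4: "A subject will have two treatment areas defined as both buttocks (left and right buttocks) OR both thighs". SAP 3.1 plans "6 subjects per region per treatment arm", so 12 per arm over both regions. Protocol 9.2 makes it the secondary objective to "assess the safety of CCH when administered using different injection techniques".

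The SAP does plan more than incidence. Section 7.8.2 adds total TEAE counts (overall and by severity), a total for events of special interest, SOC and preferred-term tables by maximum severity, drug-related events in three duration classes, and listings. Section 7.8.7 adds a bruise colour difference by arm at Days 4, 8 and 15. Exposure (SAP 7.8.1) is summarised at each treatment visit, and the schedule of events has local tolerability at every visit from Day 1.

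**The concern.** Protocol 8.3 reports treatment-related bruising in 75.1% and pain in 59.3% of 189 CCH-treated subjects in the Phase 2b study. Protocol 8.1.2 says that study treated one area over three visits. Here two areas are treated over the same number of sessions. Protocol 8.4 adds that most events resolved before the next treatment, so a reaction after a later session will often be a new event. Under the once-per-term rule that new event adds nothing to the incidence table.

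Injection volume, depth and number of aliquots could plausibly change how often a subject bruises or has pain, and not only whether it ever happens. If techniques differ mainly in recurrence, the main adverse-event tables will understate that, and the secondary objective is the comparison of techniques on safety. Exposure can also differ by arm: an area that is dimple-free at Day 22 or Day 43 is not treated (Protocol 12.5, SAP 3.6). An arm with fewer later sessions could then show a lower ever-rate for that reason alone.

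**Working it through.** The documents contain no power or precision calculation for adverse events, so there is no figure of theirs to reproduce. Two related figures check: 5 arms × 6 subjects × 2 regions = 60, and the Phase 2b percentages match whole counts of 189 (142/189 = 75.1%, 112/189 = 59.3%).

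**Step 1: rates with two areas.** Let q be the Phase 2b per-subject rate. If the two areas always react together, the ever-rate stays q. If they react independently, it is 1 − (1 − q)².

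- Bruising: 75.1% to 1 − 0.249² = 93.8%.
- Pain: 59.3% to 1 − 0.407² = 83.4%.
- Nodule, the next most frequent: 14.3% to 1 − 0.857² = 26.6%. The remaining six are lower.

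Only bruising approaches a ceiling, and only near independence. If every arm had the same rate, the chance of at least 11 of 12 subjects with bruising in a given arm is 16% (together) to 83% (independent). For pain it is 2% to 38%.

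**Step 2: ever/never against per session.** Assume equal, independent risk at each session. The risk per area and session is p = 1 − (1 − q)^(1/3), which is 0.371 for bruising and 0.259 for pain. The session risk s is p (together) or 1 − (1 − p)² (independent). The ever-rate is 1 − (1 − s)³. As an illustration, let a second technique halve the hazard: p′ = 1 − (1 − p)^0.5, which is 0.207 and 0.139.

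| Event, areas | Ever | Per session | Mean affected sessions of 3 (3s) |
|---|---|---|---|
| Bruising, independent | 93.8% v 75.1% | 60.4% v 37.1% | 1.81 v 1.11 |
| Bruising, together | 75.1% v 50.1% | 37.1% v 20.7% | 1.11 v 0.62 |
| Pain, independent | 83.4% v 59.3% | 45.1% v 25.9% | 1.35 v 0.78 |
| Pain, together | 59.3% v 36.2% | 25.9% v 13.9% | 0.78 v 0.42 |

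**Step 3: how much information each measure carries.** Power for 12 v 12 at two-sided 0.05 serves only as a yardstick. It uses Fisher's exact test for the two proportions and a t-test (simulated) on the number of affected sessions per subject.

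| Event, areas | Ever/never | One session alone | Affected sessions, pooled |
|---|---|---|---|
| Bruising, independent | 7.8% | 12.8% | 49% |
| Bruising, together | 14.3% | 6.4% | 32% |
| Pain, independent | 13.5% | 8.6% | 38% |
| Pain, together | 12.5% | 3.6% | 23% |

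A single session read alone does better than ever/never in only one of the four rows. The gain comes from pooling sessions within the subject.

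**Step 4: subjects prone to react.** Step 3 treats sessions as independent within a subject. A separate check added a subject effect on the logit scale (SD 0 to 4), calibrated to the Phase 2b rates, with the risk per area and session halved. It counted affected area-sessions out of six. For bruising, power was 13% to 21% on ever/never and 46% to 69% on the count. For pain it was 14% to 17% and 28% to 49%. For nodule it was at most 4% and 9%. The gain shrinks as subjects differ more but persists for bruising and pain. The six-cell count needs the side of each event, which the documents do not show to be recorded.

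**The case against.** A reader might infer that all common injection-site reactions sit near a ceiling in every arm. The documents do not support that. It fits bruising alone, and only if left and right areas react almost independently. The documents give rates for one Phase 2b regimen and none by technique.

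A reader might also infer that the safety outputs are purely ever/never. They are not: severity and duration tables can separate arms even where incidence is high, and the bruise-colour measure is a graded comparison of techniques for the most frequent event. Each leaves a gap, however. Severity takes the maximum over sessions, duration does not show recurrence, total events are not given by preferred term, and colour is measured at Days 4, 8 and 15 only, all after the first session. Listings hold the data without summarising them by arm. Table shells are in SAP Module 2, which is not among the documents, but the text of 7.8.2 does not call for a by-session table.

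On the absolute scale, ever/never often separates arms more than one session does: 25 points against 16 for bruising with areas reacting together, and 24 against 19 for pain with independent areas. That stands. It is why a by-session table without a pooled per-subject measure would add little.

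A by-session table also cannot cleanly show an effect of repeat exposure. Visits follow the first session on Days 4, 8, 15 and 22, but the next scheduled visit is Day 43 after the second session and Day 71 after the third. Later sessions also depend on remaining dimples. This stands too, and limits what may be read from the table.

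Finally, the study is exploratory, has no sample-size calculation and defines no safety test. With 12 per arm, 9/12 has a 95% interval of 43% to 95%. Small numbers limit the comparison at least as much as the counting rule does.

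**Conclusion.** The point holds for bruising and pain. The rule pools up to three sessions into one yes/no per preferred term, no planned preferred-term table recovers recurrence, and recurrence bears on the technique comparison. Under an illustrative halved hazard with 12 subjects per arm, pooled affected sessions per subject carry clearly more information (23% to 49% power) than ever/never (8% to 14%). A single session alone gives 4% to 13%. For the other listed reactions, at most about 27% per subject, there is no ceiling and little to gain.

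The sizes rest on four assumptions: Phase 2b rates transfer to this trial, areas lie somewhere between reacting together and independently, session risk is constant, and the halving is only an example. The existing tables are not wrong. This is a useful, optional addition.

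**What to change.** Keep all tables in SAP 7.8.2 and add one descriptive table of injection-site TEAEs by arm and preferred term, with two parts:

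- **(a) Incidence per treatment session.** An event belongs to a session if its onset falls from that injection date to the day before the next injection. For a subject's last session, use 21 days, so that the windows are nominally equal. The denominator is subjects treated at that session.
- **(b) Affected sessions per subject, out of sessions treated**, pooled over sessions. Any confidence interval should treat the subject as the cluster.

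Compare arms within session. Add a footnote that differences across sessions are not to be read as an effect of repeat exposure without caveat, because visits are denser after the first session and later treatment depends on remaining dimples. A split by area is possible only if the eCRF records side.

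The cost is one extra table. The SAP already derives AE onset day (Table 12) and summarises subjects treated at each visit (7.8.1), so no new data are needed. Precision will remain low with 12 subjects per arm.
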